The intervention being evaluated in this randomised trial, NEL will be carried out in addition to insertion of a temporising device (Arm A - Intervention). In our experience and in published studies, the additional risks of endoscopic lavage are low, and occur in less than 5% of cases

(21-25). The risks relate to standard neuro-endoscopic surgery and are expected to be lower than the risks of DRIFT. These include infection, further haemorrhage within the ventricles, haemorrhage related to ventricular decompression, seizures, CSF leak, electrolyte disturbance and a <1% risk of brain injury (21-25). These risks are not expected to be significantly higher than insertion of a temporising device alone. In theory the risk of electrolyte disturbance and seizures, related to the presence of lavage fluid within the ventricles, is slightly higher than with insertion of a temporizing device. This will be mitigated by use of warm Ringer lactate solution or artificial CSF, and by monitoring of serum electrolytes post-lavage. These infants are routinely cared for within a neonatal intensive care unit environment and close care and supervision is routine.

Several published studies have suggested that the requirement for permanent CSF diversion through a ventricular peritoneal shunt is reduced after lavage compared to insertion of a temporising device alone (22,24,25). This is a potential additional advantage of NEL that will be evaluated as an exploratory outcome.

The risks associated with NEL will be mitigated by ensuring that patient recruitment will only take place in established paediatric neurosurgical units and will be undertaken by paediatric neurosurgeons who routinely perform a range of neuro-endoscopic procedures. Each paediatric neurosurgical unit is affiliated with a neonatal unit to ensure appropriate neonatal care. A number of meetings have taken place to discuss the technical details of the irrigation procedure, and a surgical consensus statement has been published (28). In addition, a meeting with world experts in endoscopic lavage in this population is planned before commencement of recruitment to enable a wider discussion and sharing of operative nuances, experience and knowledge.

2 Selection of Sites/Investigators

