4.1 Introduction

Randomisation will be carried out immediately prior to surgery (after the participating infant is taken to theatre). Eligible participants will be randomly assigned in a 1:1 ratio to:

Arm A - NEL with temporising device (Intervention) OR

Arm B - temporising device alone (Control).

Parents and guardians will not be aware of the allocated arm prior to the surgery. They will be informed which procedure has been performed after the surgery.

Both the intervention (Arm A) and control arm (Arm B) procedures will be performed by paediatric neurosurgeons who have experience in infant neuro-endoscopy. Although novel in this context, NEL is not a new procedure to neurosurgeons, who will have experience in endoscopic procedures and lavage for a range of indications as part of standard of care treatment.

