5.1.2 Secondary Outcomes

The secondary outcome measures are:

- 1. Developmental Measures:
 - a. Motor quotient (MQ): Age equivalent motor score of the Bayley IV divided by corrected age at assessment, measured at 2 years' corrected age
 - b. Language quotient (LQ): Age equivalent language score of the Bayley IV divided by corrected age at assessment, measured at 2 years' corrected age
- 2. Other neurological and functional assessments conducted during the 2-year follow-up visit:
 - a. Presence of seizures during the first 2 years and use of anticonvulsant medication at 2 years.
 - Presence of cerebral palsy (+ accompanying Gross Motor Function Classification System (GMFCS) grade and deficit distribution map using the Classification of SCPE
 - c. Assessment of hearing and vision (British Association of Perinatal Medicine classification)
 - d. Parent report:
 - i. Brief Infant Toddler Social Emotional Assessment (BITSEA)
 - ii. Quantitative Checklist for Autism in Toddlers (Q-CHAT)
- 3. Mortality up to 2 years corrected age.
- 4. NEL & VP shunt related outcomes:

- a. Safety of NEL: Number of Adverse Events, where Adverse Events would include (and not limited to) secondary bleeding in the brain, post-operative infections, temporising device survival, mortality, stroke, seizures, electrolyte disturbances, CSF leak, unexpected readmissions or return to theatre.
- b. Number and type of further surgical procedures, including revision of the temporising drainage device (VAD or VSG), addition of a second temporising device, surgery for loculated or isolated ventricles, and revisions of the VP shunt, if implanted, until two years' corrected age. These infants often need multiple shunt revisions during their first two years of life. We will have a separate CRF to record data related to these unexpected presentations and procedures.
- c. Requirement for permanent VP shunt insertion at 6 months' corrected age. (This is at the discretion of the treating team in the participating centre, according to routine clinical care).
- 5. Quality of life and health economic assessments:
 - a. Health-Related Quality of Life (HRQoL) in children: TNO-AZL Preschool Children's Quality of Life (TAPQOL) to be assessed at 12-months and 2 years' corrected age
 - b. HRQoL in primary caregiver: EuroQoL EQ-5D-5L to be assessed at baseline, 6 months, 12 months- and 2 years' corrected age

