6.1.1 Adverse Events

Adverse events include:

- an exacerbation (i.e., increase in the frequency or intensity) of a pre-existing illness, episodic event or symptom (initially recorded at the screening/baseline visit), that is detected after trial intervention
- occurrence of a new illness, episodic event or symptom, that is detected after trial intervention

Adverse events do NOT include:

- Medical or surgical procedures: the condition that leads to the procedure is the adverse event
- Pre-existing disease or a condition present before treatment that does not worsen
- Hospitalisation where no untoward or unintended response has occurred

Reporting of Adverse Events

The patient population includes preterm infants who are cared for on a neonatal intensive care for a prolonged period. Due to the nature of the patient population, a high incidence of adverse events can be foreseeable during their hospital stay. Only adverse events deemed as serious (see section 6.1.2) or as notifiable event (see section 6.2) will be recorded for the trial.

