6.1.2 Serious Adverse Events

6.1.2.1 Foreseeable (expected) SAEs

The following are 'Foreseeable SAEs' that could be reasonably anticipated to occur in this population of infants during the course of the trial or form part of the outcome data.

They do not require expedited reporting by trial centres as SAEs **unless considered causally related** to the intervention (NEL) in which case they should be reported within 24 hours of site staff becoming aware of them as detailed in section 6.3.2.

'Foreseeable SAEs' that are **casually related** to the trial intervention (NEL) should be reported within 24 hours of site staff becoming aware of them using the SAE report form.

Foreseeable SAEs that are **not considered causally related** to the trial intervention (NEL) should be reported within 5 working days. Therefore, all Foreseeable SAEs occurring for patients in Arm B (Temporising device alone) will be not related to NEL and should be reported within 5 days.

Foreseeable SAEs:

- Necrotising enterocolitis or gastrointestinal perforation
- Intracranial abnormality (intraventricular haemorrhage or white matter damage) on cranial ultrasound scan or other imaging
- Seizures outside of 48 hours the procedure
- Pulmonary hypertension
- Hydrocephalus
- Respiratory distress syndrome
- Bronchopulmonary dysplasia or chronic lung disease
- Retinopathy of prematurity
- Early or late-onset Sepsis
- Patent ductus arteriosus (PDA)
- Pulmonary haemorrhage
- Pneumothorax
- Anaemia
- Hyperbilirubinaemia/jaundice
- Hypoglycaemia
- Hyperglycaemia
- Coagulopathy
- Liver cholestasis
- Liver failure
- Hypotension
- Hypertension
- Impaired renal function
- Extravasation injury
- Fractures
- Return to hospital for suspected or actual shunt malfunction or other neonatal condition unrelated to hydrocephalus after discharge from the neonatal unit, (unless readmission following initial discharge from hospital for grade 3 and above events)

6.1.2.2 'Unforeseeable SAEs' – (All SAEs not listed as 'Foreseeable SAEs')

All other SAEs occurring in trial participants which are not listed as Foreseeable SAEs in Section 6.1.2.1 are classed as unforeseeable SAEs and must be reported immediately after site staff become aware of the event (in no circumstances should this notification take longer than 24 hours) (see section 6.3).

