6.2 Notifiable Adverse Events

The following adverse events should be reported within 5 working days using the Notifiable AE CRF:

- 1. New bleed identified on post-operative cranial ultrasound (CTCAE grade 2 and above)
- 2. Unexpected return to theatre for temporising device dysfunction, infection or CSF leak (CTCAE grade 3 and above). CSF infections will be monitored closely and reviewed at Trial Management Group meetings.
- 3. Return to theatre for insertion of an additional temporising device to treat loculated hydrocephalus (CTCAE grade 3 or above) or for a second endoscopic procedure to deloculate the ventricles
- 4. Confirmed or presumed infection associated with the trial procedure (grade 3 and above). This will include superficial (wound) and deep (CNS) infection. Confirmed infection will be where a micro-organism thought to be causative is isolated and presumed is when a micro-organism is not isolated, but the treating clinical team commences antibiotics. Of note, preterm infants may have many sources of infection and the **reporting here is confined to infection associated with the procedure (grade 3 and above).**
- 5. New development of seizures within 48 hours of the intervention (NEL) (grade 3 and above)
- 6. New development of focal neurological deficits within 48 hours of the intervention (NEL) (grade 3 and above)
- 7. Abandoned NEL procedure

Only non-serious AEs which constitute a notifiable event (listed above) should be reported to CCTU (via the trial database) within 5 working days.

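### Grade 3+ seizures and focal deficits are notifiable only after NEL, so non-serious ones are counted in Arm A and not in Arm B

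*Protocol*

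**What the plan says.** Section 6.2 lists the adverse events that sites must notify within 5 working days. Item 5 is "New development of seizures within 48 hours of the intervention (NEL) (grade 3 and above". Item 6 is "New development of focal neurological deficits within 48 hours of the intervention (NEL) (grade 3 and above".

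The control arm does not receive that procedure: section 4.1 describes it as "Arm B - temporising device alone (Control". Section 6 uses the term in the same sense, since 6.1.2.1 states that "all Foreseeable SAEs occurring for patients in Arm B (Temporising device alone) will be not related to NEL and should be reported within 5 days".

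Section 6.1.1 limits what reaches the database: "Only adverse events deemed as serious (see section 6.1.2) or as notifiable event (see section 6.2) will be recorded for the trial". Section 6.4 repeats the limit for reporting to the trials unit; other non-serious events go only into the medical notes.

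The outcome that draws on these data is secondary outcome 4a in section 5.1.2: "Safety of NEL: Number of Adverse Events, where Adverse Events would include (and not limited to) secondary bleeding in the brain". Its list goes on to name stroke and seizures.

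Neighbouring text is arm-neutral. Item 4 of section 6.2 ties infection to the trial procedure, and the foreseeable-SAE list in 6.1.2.1 defines late seizures by their distance from the procedure. Neither mentions NEL.

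**The concern.** A count of adverse events compares two arms fairly only if the same event, at the same time after surgery, is recorded under the same rule in both. Items 5 and 6 start their 48-hour window at a procedure that only Arm A undergoes. Read literally, no Arm B infant can meet them.

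Safety of NEL is part of the stated objective (section 1.2). Section 4.3 lists seizures among the risks of the control procedure, and section 1.4 expects NEL to add to that risk: "In theory the risk of electrolyte disturbance and seizures, related to the presence of lavage fluid within the ventricles, is slightly higher". Seizures are thus an event for which equal ascertainment matters most. The IDMC also weighs benefit against risk on the accumulating safety reports (section 8.3.3), so unequal capture would reach monitoring during the trial as well as the final report.

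**Working it through.** The protocol gives no figure for this point, so there is none to reproduce. The check has two steps.

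**Step 1: follow one event through the rules.** Take a new grade 3+ seizure or focal deficit 24 hours after surgery.

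| Site's judgement | Arm A | Arm B |
|---|---|---|
| Serious | Unforeseeable SAE, 24 hours (6.1.2.2, 6.4) | Unforeseeable SAE, 24 hours (6.1.2.2, 6.4) |
| Non-serious | Notifiable event, 5 working days (6.2, items 5 and 6) | Not notifiable, so not recorded (6.1.1) |

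The first row holds because neither a seizure inside 48 hours nor a focal deficit is on the foreseeable list. The arms differ only in the second row. Items 1 to 4 of section 6.2 are not tied to NEL. Item 7, an abandoned NEL, can by its nature occur only in Arm A.

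**Step 2: size the gap.**

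Inputs:
- n = 50 infants per arm (section 3.3).
- r = true 48-hour rate of these grade 3+ events, taken as equal in both arms. This is an assumption. Sections 1.4 and 4.3 put complications below 5%, but without a grade or a 48-hour limit, so 5% is only a reference point; 2% and 10% give a range.
- s = share of events judged serious. The protocol does not give it, so it runs from 0 to 1.

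Formulas:
- Expected recorded events: Arm A = n × r; Arm B = n × r × s; gap = n × r × (1 − s).
- Recorded counts: Arm A ~ Binomial(50, r) and Arm B ~ Binomial(50, r × s), independent, with at most one event per infant.

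At r = 5% and s = 0.5: Arm A = 50 × 0.05 = 2.5; Arm B = 50 × 0.05 × 0.5 = 1.25; gap = 1.25.

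At r = 5% and s = 0, Arm B is always zero, so P(A > B) = 1 − 0.95^50 = 0.923.

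| r | s | Expected A vs B | P(A > B) | P(B > A) |
|---|---|---|---|---|
| 2% | 0 | 1.0 vs 0 | 0.636 | 0 |
| 2% | 0.5 | 1.0 vs 0.5 | 0.472 | 0.180 |
| 2% | 0.9 | 1.0 vs 0.9 | 0.368 | 0.314 |
| 2% | 1 | 1.0 vs 1.0 | 0.345 | 0.345 |
| 5% | 0 | 2.5 vs 0 | 0.923 | 0 |
| 5% | 0.5 | 2.5 vs 1.25 | 0.651 | 0.170 |
| 5% | 0.9 | 2.5 vs 2.25 | 0.450 | 0.359 |
| 5% | 1 | 2.5 vs 2.5 | 0.406 | 0.406 |
| 10% | 0 | 5.0 vs 0 | 0.995 | 0 |
| 10% | 0.5 | 5.0 vs 2.5 | 0.779 | 0.122 |
| 10% | 0.9 | 5.0 vs 4.5 | 0.499 | 0.366 |
| 10% | 1 | 5.0 vs 5.0 | 0.433 | 0.433 |

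With no true difference between arms, any s below 1 tilts the recorded count against NEL. With items 5 and 6 tied to the index procedure, capture is the same in both arms whatever s is; at r = 5% that is 2.5 vs 2.5, with a chance of 0.406 for each arm to show the higher count.

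**The case against.** The strongest reply is that few events fall into the gap. Items 5 and 6 start at grade 3, which section 6.4.1.2 describes in terms of severity, hospital stay and disability. Those overlap heavily with the seriousness criteria in Table 4, whose notes name seizures without hospitalisation as a possible important medical event. If nearly all such events are judged serious, s is close to 1 and little is lost. This stands. It limits the size but does not remove the asymmetry: items 5 and 6 add something to SAE reporting only for events judged non-serious, and for those they work in one arm. Capture in Arm B also then rests on a seriousness judgement by site staff who know the allocation.

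There is back-up in both arms: adverse event and anti-epileptic medication review at surgery and at 24-48 hours, post-operative ultrasound, and seizures over the first two years as a separate secondary outcome. None of these gives a graded 48-hour count, and focal deficits are covered less well than seizures.

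A reader might infer more than the text supports:

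- **That Arm B has no capture of these events.** It has the 24-hour SAE route, whatever the cause.
- **That the rule could hide harm from NEL.** The tilt is the other way.
- **That judging causality against NEL distorts outcome 4a.** That outcome counts adverse events, not related ones, and an arm without NEL has no NEL-related events by definition. Causality affects how fast an event is reported, not whether an SAE is counted.
- **That electrolyte disturbance has the same defect.** It is on neither list, but this is equal between arms. Sodium and potassium are collected at baseline and at 24-48 hours in both arms, and deriving a count from them is a matter for the analysis plan.

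**Conclusion.** The point holds in a limited form. Items 5 and 6 of section 6.2 conflict in wording with item 4 and with section 6.1.2.1. Together with section 6.1.1, they make the recording of non-serious grade 3+ seizures and focal deficits depend on the arm. The expected gap is n × r × (1 − s) events against NEL. At an assumed r of 5% it is 2.5 events if none are serious, 1.25 if half are, 0.25 if 90% are, and zero if all are. This rests on equal true rates, sites following the wording literally, and assumed values of r and s.

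The primary outcome, deaths, serious events and items 1 to 4 are unaffected. It is worth correcting because an analysis plan cannot restore events that were never entered; they would have to be sought in the medical notes.

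A related conflict needs reconciling, although it does not alter the count. Sections 6.1.2.1 and 6.4.1.3 refer causality to NEL alone, whereas section 6.4 asks for 24-hour reporting of foreseeable SAEs related to NEL or to trial procedures. A foreseeable SAE attributed to device insertion in Arm B thus has a 5-day limit in one place and a 24-hour limit in another.

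**What to change.** 1. In section 6.2, items 5 and 6, replace the reference to the intervention (NEL) with: *the index trial procedure (NEL with temporising device, or temporising device alone)*. Make the same change on the Notifiable AE CRF.
2. Reconcile the causality reference in sections 6.1.2.1 and 6.4.1.3 (NEL only) with section 6.4 (NEL or trial procedures), so that a foreseeable SAE in Arm B has one reporting route.

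The cost is a protocol amendment, a small CRF change and a few more notifications from sites for Arm B infants. No visit or test is added. If infants were randomised before the change takes effect, their 48-hour events in Arm B would have to be checked against the medical notes for the count to be comparable throughout.

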6.3 Decision for withdrawal of all Medical Care

There may be a small number of cases where the decision is made to withdraw all medical care, resulting in participant death. If this occurs after the time of randomisation, an SAE report should be submitted immediately after site staff become aware of the event (in no circumstances should this notification take longer than 24 hours) (see section 6.3). All infant deaths will be reported to the IDMC promptly, as and when they are reported to CCTU, to review on a case-by-case basis

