The following assessments will be performed by a qualified and validated independent clinical development specialist **blinded to the treatment arm.** This specialist will be independent from the trial team and the visit may take place outside of the neurosurgical unit (e.g., in a clinic room at local hospital). The arrangements for this visit will be coordinated by UCL CCTU with the site research teams and independent clinical development specialist.

- Bayley Scales of Infant and Toddler Development (4th edition) (Bayley IV)
- Cerebral palsy assessment, CP subtype (SCPE) & Gross Motor Function Classification System (GMFCS) grade
- Vision and hearing assessment (BAPM classification)

Unscheduled Visits to Neurosurgical Unit

Additional visits (unscheduled visits) will be performed as deemed clinically necessary (i.e. all returns to the neurosurgical unit occurring in between scheduled visits until completion of 2-year follow-up). These unscheduled visits must be clearly documented in the participants medical notes. Sites are encouraged to undertake the following assessments:

- Clinical Assessment
- Physical examination

- Wound site check
- Head circumference
- Review of Shunt/Temporising Device information
- Review of Adverse Events. Note: All incidences of unexpected return to theatre for temporising device dysfunction, infection or CSF leak (CTCAE grade 3 and above) must be reported as a Notifiable Adverse Event (see section).
- MRI scan if performed as standard of care assessment only
- Optional CSF Sample Collection (see Appendix 1 and Laboratory Sample Management Plan for further details).
- Optional Research Blood Sample Collection (see Appendix 1 and Laboratory Sample Management Plan for further details).

4 Trial Intervention

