6.1 Definitions

Definitions of harm of the EU Directive 2001/20/EC Article 2 based on the principles of GCP apply to this trial.

Table 4: Definitions

Table 4. Delililions	
Adverse Event (AE)	Any untoward medical occurrence in a study participant,
	which does not necessarily have a causal relationship with
	the study intervention (NEL).
Notifiable Adverse Event	Any AE that:
(NAE)	•is listed in section 6.2 (Notifiable Adverse Events)
	These events should be reported within 5 working days of
	site becoming aware.
Serious Adverse Event	Any AE that:
(SAE)	results in death
	• is life threatening*
	requires hospitalisation or prolongs existing
	hospitalisation**
	results in persistent or significant disability or incapacity
	is a congenital anomaly or birth defect
	or is another important medical condition***
Foreseeable (Expected)	Any AE that:
SAE	results in death
	• is life threatening*
	requires hospitalisation or prolongs existing
	hospitalisation**
	results in persistent or significant disability or incapacity
	is a congenital anomaly or birth defect
	or is another important medical condition***
	AND
	•is listed in section 6.1.2 (Foreseeable Adverse Events)
	These events must be reported within 5 days of site
	becoming aware if there is no causal relationship to trial
	intervention (NEL)
	These events must be reported within 24 hours of site
	becoming aware if causally related to trial intervention
	(NEL).
Unforeseeable	Any AE that:
(unexpected) SAE	results in death
	• is life threatening*
	requires hospitalisation or prolongs existing

hospitalisation**

- results in persistent or significant disability or incapacity
- is a congenital anomaly or birth defect
- or is another important medical condition***

AND

•is **not** listed in section 6.1.2 (Foreseeable Adverse Events)

These events must be reported within 24 hours of site becoming aware if causally related or unrelated to trial intervention (NEL).

- * The term life threatening here refers to an event in which the patient is at risk of death at the time of the event; it does not refer to an event that might hypothetically cause death if it was more severe (e.g., a silent myocardial infarction)

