6.4.1.2 Severity or Grading of Adverse Events

The severity of all AEs (serious and non-serious) in this trial should be graded using the gradings in the Common Terminology Criteria for Adverse Events (CTCAE) Version 5.0 (2017):

Grades for AEs according to the CTCAE are:

Grade 1: Mild; asymptomatic or mild symptoms; clinical diagnostic observations only; intervention not indicated.

Grade 2: Moderate; minimal, local or non-invasive intervention indicated.

Grade 3: Severe or medically significant but not life threatening; hospitalisation or prolongation of hospitalisation indicated; disabling.

Grade 4: Life threatening consequences; urgent intervention indicated.

Grade 5: Death related to AE.

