6.5 Safety Monitoring

The Independent Data Monitoring Committee (IDMC) will review the study data and outcomes including SAEs. All infant deaths will be reported to the IDMC promptly, as and when they are reported to CCTU, to review on a case-by-case basis. The IDMC will ensure the safety and wellbeing of the trial participants and, if appropriate, make recommendations to the Trial Steering Committee (TSC) regarding continuance of the study or modification of the Protocol. The TSC will have ultimate responsibility for deciding whether the trial should be stopped on safety grounds.

CCTU will also provide safety information to the Trial Management Group on a periodic basis. Notifiable events including CSF infections will be monitored closely and reviewed at TMG meetings.

Trial Intervention (NEL) compliance:

Non-compliance with the intervention (NEL) is not anticipated but trial data will be reviewed on a monthly basis and post-operative ultrasound scans, will be reviewed at least quarterly by the TMG to evaluate any variability in the surgical procedures.

Where necessary, feedback will be given to the PI at the participating site regarding their operative technique and radiographic outcome. Any relevant issues will be discussed with the participating unit.

7 Quality Assurance & Control

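### The safety section gives contradictory reporting clocks (24 hours, 5 days or 5 working days) for the same death or life-threatening event

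*Protocol*

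**What the plan says.** **Deaths and the IDMC.** Section 6.3 (Decision for withdrawal of all Medical Care) requires an SAE report when a death follows withdrawal of care after randomisation: "in no circumstances should this notification take longer than 24 hours". It then says "All infant deaths will be reported to the IDMC promptly, as and when they are reported to CCTU". Section 6.5 repeats that deaths go to the IDMC "promptly, as and when they are reported to CCTU, to review on a case-by-case basis".

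**Foreseeable SAEs.** Table 4 in section 6.1 defines a foreseeable SAE as an adverse event that meets a seriousness criterion, death and threat to life included, and is on the section 6.1.2 list. For those with no causal relationship to NEL it says "These events must be reported within 5 days of site" (the sentence goes on to the site becoming aware). The Glossary gives the same period. Section 6.1.2.1 gives 5 working days for unrelated events and then says that foreseeable SAEs in Arm B "will be not related to NEL and should be reported within 5 days". Sections 6.4.1.1 and 6.4.2.1 give 5 working days. None of these exempts deaths. Section 6.4 requires 24 hours for foreseeable SAEs related to NEL or to trial procedures.

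**Notifiable events.** Section 6.2 opens with "The following adverse events should be reported within 5 working days using the Notifiable AE CRF" and closes by limiting this route to non-serious events; section 6.4 repeats the limit. Section 3.6, on unscheduled visits, says that "unexpected return to theatre for temporising device dysfunction, infection or CSF leak (CTCAE grade 3 and above) must be reported as a Notifiable Adverse Event". Section 6.4.2.1 sends all notifiable events to the 5-working-day form. Neither carries the limit. Section 6.4.1.2 defines "Grade 4: Life threatening consequences; urgent intervention indicated", and grade 5 as death.

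**The concern.** A site with a serious event needs one answer to how soon it must report. Here the answer depends on which section the site reads and, for some events, on the arm. The 6.1.2.1 list includes sepsis, necrotising enterocolitis, pulmonary haemorrhage, liver failure and intraventricular haemorrhage, all of which can be fatal in preterm infants, so the slow route is open to real deaths.

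The IDMC is to consider each death case by case and advise on continuation, but it hears of a death only once CCTU does. Any slack in the site's clock is therefore passed on to safety oversight, in a trial of a surgical procedure in preterm infants.

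**Working it through.** The protocol states no figure to reproduce. The check sets the rules side by side and then sizes the delay.

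**Step 1. The site-to-CCTU clock, case by case**

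| Event (fatal or life-threatening) | Rule | Clock |
|---|---|---|
| Not on the 6.1.2.1 list, either arm | 6.1.2.2, 6.4, 6.4.2.1 | 24 hours |
| Listed, Arm A, judged related to NEL | Table 4, 6.1.2.1, 6.4 | 24 hours |
| Listed, Arm A, judged unrelated | Glossary, Table 4 | 5 days |
| The same | 6.1.2.1, 6.4.1.1, 6.4.2.1 | 5 working days |
| Listed, Arm B | 6.1.2.1 | 5 days, always |
| Listed, Arm B, related to a trial procedure | 6.4 | 24 hours |
| Death after withdrawal of care, either arm | 6.3 | 24 hours |

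**Step 2. Where one event meets two rules**

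(a) Take an infant who dies after care is withdrawn because of listed sepsis unrelated to NEL. Section 6.3 gives 24 hours; sections 6.1.2.1, 6.4.1.1 and 6.4.2.1 give 5 working days; Table 4 gives 5 days.

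(b) Take an Arm B infant with a listed serious event attributed to insertion of the temporising device. Section 6.1.2.1 gives 5 days because the event cannot be related to NEL. Section 6.4 gives 24 hours if the operation is a trial procedure, and the paragraph on Protocol Treatment Discontinuation in section 4 describes the trial procedure as either arm's operation. Section 6.4.1.3 and Table 5 assess causality against NEL only, so they provide no scale for the wider trigger.

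(c) Take a life-threatening infection that needs an unexpected return to theatre. It is grade 4, so it is above the grade 3 threshold and is a notifiable event under section 3.6, with 5 working days under section 6.4.2.1. It is also serious under Table 4. Unless it is recorded as sepsis it is not on the 6.1.2.1 list, so sections 6.1.2.2 and 6.4.1.1 give 24 hours.

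**Step 3. Size of the delay**

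Five working days plus one weekend is 5 + 2 = 7 calendar days, without public holidays. The alternative is 1 day.

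Section 1.3 plans 100 infants over 3 years. Average spacing of randomisations: 36 months × 30.4 days ÷ 100 = 10.9 days. Expected further randomisations before CCTU hears:

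- 7-day clock: 7 ÷ 10.9 = 0.64
- 1-day clock: 1 ÷ 10.9 = 0.09

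Assuming a constant Poisson rate, the chance that at least one more infant is randomised in the gap is 1 − exp(−0.64) = 47% for 7 days and 1 − exp(−0.09) = 9% for 1 day. These figures take the full time allowed; sites may report sooner.

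**The case against.** **The IDMC sentence is not contradicted.** A reader might infer that the slow clock conflicts with prompt IDMC review of every death. It does not: the protocol counts promptness from receipt at CCTU, so the sentence is met under either site clock. This stands. The fault lies upstream of that sentence.

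**No bias against NEL is shown.** A reader might infer that control deaths reach the IDMC systematically later. Table 5 calls an event related only on clear evidence with other contributing factors ruled out, so most Arm A deaths from listed causes would take the same slow route. Section 8.3.3 plans no formal interim analysis, and a lag of days cannot alter the final comparison. This stands too.

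**Serious events are already kept off the notifiable form.** Sections 6.2 and 6.4 limit that form to non-serious events, and section 6.4.1.1 makes seriousness the first question. This largely answers case (c), and a site could file both forms. What remains is that sections 3.6 and 6.4.2.1 omit the limit while the threshold includes grades 4 and 5, which always meet Table 4's seriousness criteria.

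**The specific rule governs.** A site could let section 6.3 override the general rule for withdrawal-of-care deaths. That is sensible, but the protocol does not say so, and it leaves other deaths from listed causes on the slow clock.

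**Death is not a listed term, so every death is unforeseeable.** Table 4 applies the list to the event that results in death, so this reading fails.

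**Slower reporting is deliberate.** Section 6.1.1 explains that many adverse events are expected in these infants. That supports a slow route for anticipated events; it does not explain different clocks for the same event.

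**Conclusion.** The point holds as a set of internal contradictions. A fatal or life-threatening listed event judged unrelated to NEL may wait 5 days or 5 working days, with no exception for deaths, while section 6.3 caps some of the same deaths at 24 hours. Sections 6.1.2.1 and 6.4 use different causality triggers, which matters for Arm B. The slow route has two time units. The gap on notifiable events is the weakest part and needs only a repeated qualifier.

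In practice the IDMC may first learn of some deaths about a week after the site knew, with every rule kept. At the planned average rate, and if the full time is used, there is roughly an even chance (47%) that another infant is randomised meanwhile, against 9% with a one-day clock. This rests on steady recruitment to target and no public holidays. It measures delayed oversight; it does not measure harm, and it does not show that the IDMC would have acted differently.

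**What to change.** Reconcile the Glossary, section 3.6, Table 4, and sections 6.1.2.1, 6.3, 6.4, 6.4.1.1 and 6.4.2.1:

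1. State one clock for deaths and life-threatening events that does not depend on arm or on the 6.1.2.1 list. Section 6.3 already applies 24 hours to some deaths, so extending that rule would need the least new text.
2. Use one causality trigger, NEL or trial procedures, throughout. Reword the Arm B sentence in section 6.1.2.1 to agree, and make Table 5 cover the same trigger.
3. Repeat the non-serious limit in sections 3.6 and 6.4.2.1, and say that a notifiable event which is also serious takes the SAE clock.
4. Use one time unit for whatever stays on the slow route.

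The Appendix II flowchart should be checked against the agreed wording. The cost is an amendment to the safety wording, a notice to sites, and a few faster reports a year. Design, sample size and analysis are unaffected.
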